Appendix 8 (cont.): WHO Toxicity Grading Scale for Determining the Severity of Adverse Events

CHEMISTRIES				
Hyponatremia	130–135 mEq/L	123–129 mEq/L	116–122 mEq/L	< 116 or mental status changes or seizures
Hypernatremia	146–150 mEq/L	151–157 mEq/L	158–165 mEq/L	> 165 mEq/L or mental status changes or seizures
Hypokalemia	3.0–3.4 mEq/L	2.5–2.9 mEq/L	2.0–2.4 mEq/L or intensive replacement Rx required or hospitalization required.	< 2.0 mEq/L or paresis or ileus or life-threatening arrhythmia
Hyperkalemia	5.6–6.0 mEq/L	6.1–6.5 mEq/L	6.6–7.0 mEq/L	> 7.0 mEq/L or life-threatening arrhythmia
Hypoglycemia	55–64 mg/dL	40–54 mg/dL	30–39 mg/dL	< 30 mg/dL or mental status changes or coma
Hyperglycemia (note if fasting)	116–160 mg/dL	161–250 mg/dL	251–500 mg/dL	> 500 mg/dL or ketoacidosis or seizures
Hypocalcemia (corrected for albumin)	8.4–7.8 mg/dL	7.7–7.0 mg/dL	6.9–6.1 mg/dL	< 6.1 mg/dL or life-threatening arrhythmia or tetany
Hypercalcemia (correct for albumin)	10.6–11.5 mg/dL	11.6–12.5 mg/dL	12.6–13.5 mg/dL	> 13.5 mg/dL life-threatening arrhythmia
Hypomagnesemia	1.4–1.2 mEq/L	1.1–0.9 mEq/L	0.8–0.6 mEq/L	< 0.6 mEq/L or life-threatening arrhythmia
Hypophosphatemia	2.0–2.4 mg/dL	1.5–1.9 mg/dL or replacement Rx required	1.0–1.4 mg/dL intensive Rx or hospitalization required	< 1.0 mg/dL or life-threatening arrhythmia

Appendix 8 (cont.): WHO Toxicity Grading Scale for Determining the Severity of Adverse Events

CHEMISTRIES continued				
Hyperbilirubinemia	1.1–1.5 \times ULN	1.6–2.5 \times ULN	2.6–5 \times ULN	>5 \times ULN
BUN	1.25–2.5 \times ULN	2.6–5 \times ULN	5.1–10 \times ULN	>10 \times ULN
Creatinine	1.1–1.5 \times ULN	1.6–3.0 \times ULN	3.1–6 \times ULN	>6 \times ULN or required dialysis
URINALYSIS				
Proteinuria	1+ or <0.3% or <3g/L or 200 mg–1 g loss/day	2–3+ or 0.3–1.0% or 3–10 g/L 1–2 g loss/day	4+ or >1.0% or >10 g/L 2–3.5 g loss/day	nephrotic syndrome or >3.5 g loss/day
Hematuria	microscopic only	gross, no clots	gross + clots	obstructive or required transfusion
CARDIAC DYSFUNCTION				
Cardiac Rhythm		asymptomatic, transient signs, no Rx required	recurrent/persistent; no Rx required	requires treatment
Hypertension	transient inc. >20 mm; no Rx	recurrent, chronic, >20 mm, Rx required	requires acute Rx; no hospitalization	requires hospitalization
Hypotension	transient orthostatic hypotension, no Rx	symptoms correctable with oral fluids Rx	requires IV fluids; no hospitalization required	requires hospitalization
Pericarditis	minimal effusion	mild/moderate asymptomatic effusion, no Rx	symptomatic effusion; pain; EKG changes	tamponade; pericardiocentesis or surgery required
Hemorrhage, Blood Loss	microscopic/occult	mild, no transfusion	gross blood loss; 1–2 units transfused	massive blood loss; >3 units transfused

Appendix 8 (cont.): WHO Toxicity Grading Scale for Determining the Severity of Adverse Events

RESPIRATORY				
Cough	transient; no Rx	treatment-associated cough local Rx	uncontrolled	
Bronchospasm, Acute	transient; no Rx < 80%–70% FEV ₁ (or peak flow)	requires Rx normalizes with bronchodilator; FEV ₁ 50%–70% (or peak Flow)	no normalization with bronchodilator; FEV ₁ 25%–50% (or peak flow retractions)	cyanosis: FEV ₁ <25% (or peak flow) or intubated
GASTROINTESTINAL				
Stomatitis	mild discomfort; no limits on activity	some limits on eating/drinking	eating/talking very limited	requires IV fluids
Nausea	mild discomfort; maintains reasonable intake	moderate discomfort; intake decreased significantly; some activity limited	severe discomfort; no significant intake; activities limited	minimal fluid intake
Vomiting	transient emesis	occasional/moderate vomiting	orthostatic hypotension or IV fluids required	hypotensive shock or hospitalization required for IV fluid therapy
Constipation	mild	moderate	severe	distensions w/vomiting
Diarrhea	transient 3–4 loose stools/day	5–7 loose stools/day	orthostatic hypotension or >7 loose stools/day or required IV fluids	hypotensive shock or hospitalization for IV fluid therapy required

Appendix 8 (cont.): WHO Toxicity Grading Scale for Determining the Severity of Adverse Events

NEURO AND NEUROMUSCULAR				
Neuro-cerebellar	slight incoordination dysdiadochokinesis	intention tremor, dysmetria, slurred speech; nystagmus	locomotor ataxia	incapacitated
Mood	mild anxiety or depression	moderate anxiety or depression and therapy required	severe anxiety or depression or mania; needs assistance	acute psychosis; incapacitated, requires hospitalization
Neuro control (ADL=activities of daily living)	mild difficulty concentrating; no Rx; mild confusion/agitation; ADL unaffected	moderate confusion/agitation some limitation of ADL; minimal Rx	severe confusion/agitation needs assistance for ADL; therapy required	toxic psychosis; hospitalization
Muscle strength	subjective weakness no objective symptoms/signs	mild objective signs/symptoms no decrease in function	objective weakness function limited	paralysis
OTHER PARAMETERS				
Fever: oral, >12 hours	37.7–38.5 C or 100.0–101.5 F	38.6–39.5 C or 101.6–102.9 F	39.6–40.5 C or 103–105 F	>40 C or >105 F
Headache	mild, no Rx therapy	transient, moderate; Rx required	severe; responds to initial narcotic therapy	intractable; required repeated narcotic therapy
Fatigue	no decrease in ADL	normal activity decreased 25–50%	normal activity decreased >50% can't work	unable to care for self
Allergic Reaction	pruritus without rash	localized urticaria	generalized urticaria; angioedema	anaphylaxis

Appendix 8 (cont.): WHO Toxicity Grading Scale for Determining the Severity of Adverse Events

OTHER PARAMETERS (continued)				
Local Reaction	tenderness or erythema	induration < 10 cm or phlebitis or inflammation	induration > 10 cm or ulceration	necrosis
Mucocutaneous	erythema; pruritus	diffuse, maculo-papular rash, dry desquamation	vesiculation, moist desquamation, or ulceration	exfoliative dermatitis, mucous membrane involvement or erythema, multiforme or suspected Stevens- Johnson or necrosis requiring surgery

Appendix 9

Guidelines for Dosing and Monitoring Bypassing Agents for Patients on Emicizumab

The use of bypassing agents is not expected in hemophilia A patients without inhibitors. For completeness, this appendix includes guidelines provided for treatment of breakthrough bleeds in patients with inhibitors. Careful consideration of the risks and potential benefits is advised when combining emicizumab, factor VIII (FVIII), and bypassing agent.

Drugs intended to control bleeds, including bypassing agents, should be used at the lowest dose expected to achieve hemostasis. Given that circulating emicizumab may increase patients' coagulation potential, the doses required to achieve hemostasis may be lower than the FVIII or bypassing agent doses used prior to starting the study.

Caution should be taken for patients who are using recombinant activated factor VII (rFVIIa [e.g., consideration of using no more than 90 µg/kg of rFVIIa as an initial dose]).

Use of activated prothrombin complex concentrate (aPCC) or PCC in combination with emicizumab should be avoided completely in patients who have the option of using other bypassing agents to treat bleeds. In the event that aPCC/PCC is the only available bypassing agent, the lowest dose expected to achieve hemostasis should be prescribed, with no more than 50 units/kg of aPCC/PCC to be administered as an initial dose.

Other bypassing agents (e.g., Byclot®) should be avoided. In cases where such agents are the only available bypassing agent, the lowest dose expected to achieve hemostasis should be prescribed, with no more than the lowest dose described in the prescribing information to be administered as an initial dose (e.g., no more than 60 µg/kg of Byclot®).

## **STATISTICAL ANALYSIS PLAN AMENDMENT RATIONALE**

The following changes have been made:

- The non-interventional study (NIS) population has been added in order to evaluate patients who previously participated in the NIS BH29768.
- Intra-patient comparisons were added to evaluate the change in the number of treated bleeds and all bleeds over time compared with the patient's historical bleed rate for patients who participated in the NIS BH29768.
- Subgroup analyses of efficacy endpoints by inhibitor status were removed because separate efficacy outputs for patients with inhibitors and without inhibitors are already planned.

Additional minor changes have been made to improve clarity and consistency.

## 1. BACKGROUND

Hemophilia A is an X-linked recessive bleeding disorder that occurs in approximately 1 in 5000 live male births. Patients with hemophilia A have a deficiency or absence of blood coagulation factor VIII (FVIII), an essential component of the intrinsic pathway in the coagulation cascade ([Mannucci and Tuddenham 2001](#); [Franchini and Mannucci 2013](#)).

The absence or functional deficiency of FVIII leads to a lifelong bleeding tendency. Common clinical signs of hemophilia A include easy bruising; prolonged bleeding after trauma or surgery; spontaneous bleeding into joints, muscles, or soft tissues; and intracranial hemorrhage. The severity of the disease roughly correlates with the residual endogenous level of FVIII activity. Approximately 68% of people with hemophilia A have moderate (25%) or severe (43%) forms, characterized by FVIII activity levels <5% or <1%, respectively, leading to frequent bleeding events with the sequelae of musculoskeletal complications (e.g., arthropathy), local functional deficits, hemorrhagic shock, neurocognitive defects, or even death ([World Federation of Hemophilia 2015](#)).

Prophylactic FVIII replacement therapy (i.e., administered on a scheduled basis with the intent to prevent bleeds) has been proven to minimize bleeding events and complications ([Manco-Johnson et al. 2007](#)). Since the 1990s, recombinant FVIII (rFVIII) concentrates have been standard-of-care treatment options for patients with hemophilia A ([Kingdon and Lundblad 2002](#)). Current prophylactic regimens commonly use infusion therapy administered two-three times weekly; other regimens use every other day administration ([Shapiro 2013](#)).

Prophylactic FVIII replacement therapy has been recognized as superior to episodic treatment of symptomatic bleeds for several decades ([Khawaji et al. 2012](#)) and was adopted by national and international organizations as the desired treatment approach. However, the burden of treatment ([Eton et al. 2013](#), [Mair and May 2014](#)) is extraordinarily onerous, as adequate prophylaxis requires a lifetime of self-administered intravenous (IV) infusion of FVIII 3–4 times each week. In addition to the obvious toll on the quality of patients' life ([Teal et al. 2014](#)), this burden results in suboptimal care for many who elect to avoid routine prophylaxis, despite its medical advantage ([Geraghty et al. 2006](#); [Lindvall et al. 2006](#); [De Moerloose et al. 2008](#); [Collins et al. 2014](#); [Oldenburg 2015](#)). Thus, episodic therapy is a standard-of-care for many patients with hemophilia in developed countries, where approximately one-third to one-half of the patients use FVIII on-demand and avoid continuous prophylaxis.

Emicizumab (also known as ACE910 and RO5534262) is a humanized monoclonal modified immunoglobulin G4 (IgG4) antibody with a bispecific antibody structure produced by recombinant DNA technology in Chinese hamster ovary (CHO) cells. Emicizumab bridges activated factor IX (FIXa) and factor X (FX) to restore the function of missing activated factor VIII (FVIIIa) that is needed for effective hemostasis. In

patients with hemophilia A, hemostasis can be restored irrespectively of the presence of FVIII inhibitors, as emicizumab shares no sequence homology with FVIII.

In addition, emicizumab offers the possibility of subcutaneous (SC) administration, removing the need for venous access. Finally, because the pharmacokinetic properties of this antibody are expected to enable marked extension of the dosing interval to once weekly, every other week, or even less frequently, this novel compound has the potential to dramatically change the treatment of patients with hemophilia A with or without FVIII inhibitors who are in need of effective, safe and low burden prophylactic therapy.

Initial experience with emicizumab in humans was generated from one Phase I study (ACE001JP) and its ongoing extension, a Phase I/II study (ACE002JP). See the RO5543262 [Emicizumab] Investigator's Brochure for additional details on clinical studies with emicizumab. The results have also been published ([Shima et al. 2016](#); [Uchida et al. 2016](#)). Based on these compelling data, the Phase III development program in adult and pediatric patients with hemophilia A (both with and without FVIII inhibitors) was initiated. These studies are Study BH29884, which evaluates 1.5 mg/kg weekly (QW) dose in the adult and adolescent population with FVIII inhibitors; Study BH29992, which evaluates 1.5 mg/kg QW, 3 mg/kg Q2W, and 6 mg/kg Q4W in pediatric patients with inhibitors; Study BH30071, which evaluates a 1.5 mg/kg QW and 3 mg/kg every 2 weeks (Q2W) dose in the non-inhibitor population; and Study BO39182, which evaluates 6 mg/kg every 4 weeks (Q4W) in a mixed (inhibitor and non-inhibitor) population.

## **2. STUDY DESIGN**

[figure not shown]
Study YO39309 is a randomized, multicenter, open-label, Phase III clinical study will enroll patients aged 12 years or older with hemophilia A regardless of FVIII inhibitor status. Approximately 70 patients who received episodic treatment with FVIII or bypassing agents prior to study entry and experience at least 5 bleeds over the prior 24 weeks will be randomized in a 2:2:1 ratio to the following regimens:

- Arm A: Emicizumab prophylaxis at 3 mg/kg QW subcutaneously for 4 weeks, followed by 1.5 mg/kg QW subcutaneously
- Arm B: Emicizumab prophylaxis at 3 mg/kg QW subcutaneously for 4 weeks, followed by 6 mg/kg Q4W subcutaneously
- Arm C: No prophylaxis (control arm)

Randomization will be stratified according to the number of bleeds patients experienced over the last 24 weeks prior to study entry, <9 versus  $\geq 9$  (or ABR 18), to ensure a balance of patients with lower versus higher number of bleeds in all arms. All patients will continue usual episodic treatment with FVIII or bypassing agents in case of a breakthrough bleeding event.

To ensure a representative variety of patients with hemophilia A enrolled in this study to investigate the efficacy and safety profile of emicizumab in both inhibitor and non-inhibitor populations, enrollment of up to 55 non-inhibitor patients will be permitted. Study patients will be enrolled globally from China and other Asia Pacific countries. At least 60 patients will be enrolled from China and Hong Kong. The study schema is shown [Figure 1](#).

**Figure 1 Study Schema for Study YO39309**

BR = bleed rate; mo = month.

The primary efficacy analysis, defined as comparing the number of bleeds over time for patients randomized to receive prophylactic emicizumab versus no prophylaxis will be conducted after reaching the clinical cutoff, which occurs at the earliest timepoint when all randomized patients (Arms A, B, and C) have either completed 24 weeks in the study or discontinued from the study.

To obtain additional safety and efficacy data on emicizumab, patients who are randomized to the no prophylaxis arm (control arm, Arm Ccontrol) will have the opportunity to switch after 24 weeks to receive emicizumab prophylaxis at the Arm B dosing regimen (emicizumab prophylaxis at 3 mg/kg QW subcutaneously for 4 weeks, followed by 6 mg/kg Q4W). For clarity, Arm C patients during the no prophylaxis period are designated Ccontrol; whereas, after switch to emicizumab they are designated Arm Cemi. After completing at least 24 weeks of treatment with prophylactic emicizumab, patients who receive emicizumab prophylaxis (Arms A, B, or Arm Cemi after treatment switch) and derive clinical benefit will be allowed to continue emicizumab until marketing authorization as part of this study or a separate extension study, as long as they continue to derive clinical benefit and emicizumab is still in clinical development.

Those who are well controlled after 24 weeks on emicizumab (< 2 spontaneous and clinically significant bleeds) will continue treatment on their assigned emicizumab regimen; whereas, those who experience suboptimal control ( $\geq 2$  spontaneous and

clinically significant bleeds) will have the option to escalate to 3 mg/kg QW after approval from the Medical Monitor.

## **2.1           PROTOCOL SYNOPSIS**

The protocol synopsis is in [Appendix 1](#).

## **2.2           COLLECTION OF PATIENT-REPORTED DATA**

### **2.2.1       Collection of Bleed and Medication Data**

Bleed and medication data are collected through an electronic bleed and medication questionnaire (BMQ), which was developed by the Sponsor given that no standard questionnaire for collection of these data exists.

The BMQ was developed as a patient-reported measure of bleeding episodes (including start date and time, reason, type, location, and symptoms of bleeds) and hemophilia-related medication use (i.e. start date and time, reason, type, and dose of injection).

To capture bleed data, emicizumab use, and other hemophilia medication use during study treatment, patients will complete the BMQ on a handheld device that will be provided to them during the Week 1 visit at the study site. This device will remain with the patient for the duration of the study to enter bleed and medication data as soon as bleeding event occurs. In the event of no bleed or medication use, the patient should complete the questionnaire at least weekly at a minimum. In case a patient did not experience any bleeds or administer any treatments for a week, the patient is asked to log into the device and fill in the questionnaire to confirm this. These weekly entries, in addition to the bleeds and medication entries, can also be used to assess compliance. Of note, the patient is able to enter bleeds and medications for the past 8 days, including the day the entries are made. This retrospective data entry window was considered acceptable in terms of recall bias and was added in order to optimize the completeness of data collection.

Patients who withdraw from emicizumab treatment will continue to record bleeds and hemophilia medication administration until they complete the safety follow-up visit.

The patient is able to edit and delete bleeds and medications for 24 hours after they are entered. Furthermore, the investigator and patient are instructed to review the data together at every clinic visit. If the patient has been unable to enter data for any reason, the investigator is able to do so using a data clarification request (DCR; not subject to the previous 8-day data entry window). Note, the symptoms of joint and muscle bleeds are not collected in this case because the patient may not be able to reliably remember them. In addition, the investigator is able to request a change be made to the vendor's database by submitting a DCR.

Furthermore, the Sponsor's data manager and Medical Monitor review the patient entered data for clear inconsistencies against data collected on the electronic Case

Report Form (eCRF) or to identify obvious data points to be clarified (e.g., missing entry of the weekly emicizumab injection). These requests are sent to the investigator, who reviews them with the patient and may enter the data via the site data entry system or request a change to be made in the vendor's database via a DCR, if necessary.

## **2.2.2 Collection of Health-Related Quality-of-Life and Health Status Data**

At specified visits, patients will complete health-related quality-of-life (HRQoL), health status, and satisfaction/preference questionnaires on a tablet device that will remain at study sites. The instructions for completing the patient-reported outcome (PRO) questionnaires electronically will be provided by the investigator staff during the Week 1 visit at the site. The data will be transmitted automatically after entry to a centralized secure database at the vendor.

## **2.3 ENDPOINTS**

### **2.3.1 Primary Efficacy Endpoint**

Bleed rate is defined as the number of bleeds over the efficacy period. A bleed is counted in the primary analysis if it was treated with coagulation factors and fulfills the adapted International Society on Thrombosis and Haemostasis (ISTH; [Blanchette et al. 2014](#)) criteria, as described in Section 4.5.8 of the protocol. More specifically, the following rules as outlined in the sections below are applied.

#### **2.3.1.1 Efficacy Period**

The start of the efficacy period for each individual patient is defined as the first day when there is data in the BMQ. For patients starting the study on emicizumab (Arms A and B) this is expected to coincide with the Week 1 visit, and the day of their first emicizumab dose. For patients who do not start the study on emicizumab (Arm C), the start of the efficacy period should coincide with the Week 1 visit.

Of note, the first day when there is data in the BMQ, includes the first day for which data is reported via the handheld device, a DCR, or the day of device activation.

A second efficacy period is defined for patients in Arm C who switch to emicizumab starting on the day of their first emicizumab dose.

For patients randomized or enrolled on emicizumab, the end of the efficacy period is defined as the date of the clinical cutoff or the date of withdrawal from the initial study period (i.e., treatment phase according to eCRF), whichever is earlier. For patients randomized to no prophylaxis (Arm C), the end of the first efficacy period is defined as the day before the first emicizumab dose or the date of withdrawal from the initial study period (i.e., treatment phase according to eCRF) or the date of the clinical cutoff if neither of the aforementioned events has taken place. For patients whose dose is up-titrated, the efficacy period on the initial dose (the initial period for patients randomized to Arms A and B; the second efficacy period, starting at first emicizumab

dose for patients randomized to Arm C) ends 1 day prior to the first day on the up-titrated dose.

For patients who withdraw from the study before reaching the Week 1 visit, the duration of the efficacy period is set to 1 day, and it starts and ends on the same day of randomization/enrollment.

For patients whose dose is up-titrated, the bleeds on the up-titrated dose are analyzed separately. The efficacy period on a given up-titrated dose (second efficacy period for patients randomized to Arms A and B; third efficacy period for patient randomized to Arm C) starts with the first day on this dose and ends on the day of the clinical cutoff or the date of withdrawal.

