4.1.1 Inclusion Criteria

4.1.1.1 Arms A, B, and C

Patients in Arms A, B, and C must meet the following criteria for study entry:

- Signed Informed Consent Form by the patient or a legal guardian
- Able to comply with the study protocol, in the investigator's judgment
- Willingness and ability to comply with scheduled visits, treatment plans, laboratory tests, and other study procedures, including the completion of PRO questionnaires and bleed and medication diary through the use of an electronic device
- Aged 12 years or older at the time of informed consent
- Body weight $\geq 40 \text{ kg}$ at the time of screening
- Diagnosis of severe congenital hemophilia A (intrinsic FVIII level $< 1\%$) or hemophilia A with FVIII inhibitors
- Patients without FVIII inhibitors ($< 0.6 \text{ BU/mL}$) who completed successful ITI must have done so at least 5 years before screening and have no evidence of inhibitor recurrence (permanent or temporary) indicated by detection of an inhibitor $> 0.6 \text{ BU/mL}$ since ITI (Antun et al. 2015)
- Documentation of the details of episodic therapy (FVIII or bypassing agents) and of number of bleeding episodes for at least the last 24 weeks

- ≥ 5 bleeds in the last 24 weeks prior to study entry
- Adequate hematologic function, defined as platelet count $\geq 100,000/\mu\text{L}$ and hemoglobin $\geq 8 \text{ g/dL}$ (4.97 mmol/L) at the time of screening
- Adequate hepatic function, defined as total bilirubin $\leq 1.5 \times$ the upper limit of normal (ULN; excluding Gilbert's syndrome) and AST and ALT $\leq 3 \times$ ULN at the time of screening; no clinical signs or known laboratory/radiographic evidence consistent with cirrhosis
- Adequate renal function, defined as serum creatinine $\leq 2.5 \times$ ULN and creatinine clearance by Cockcroft-Gault formula $\geq 30 \text{ mL/min}$
- For women of childbearing potential: agreement to remain abstinent (refrain from heterosexual intercourse) or use a contraceptive method with a failure rate of $< 1\%$ per year during the treatment period and for at least 5 elimination half-lives (24 weeks) after the last dose of study drug

A woman is considered to be of childbearing potential if she is postmenarcheal, has not reached a postmenopausal state (≥ 1 year of amenorrhea with no identified cause other than menopause), and has not undergone surgical sterilization (removal of ovaries and/or uterus).

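### The first efficacy period opens on the first day with diary data, with no floor at first dose or Week 1, so back-dated pre-treatment bleeds can be counted

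*SAP*

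**What the plan says.** SAP 2.3.1.1 sets the start: "The start of the efficacy period for each individual patient is defined as the first day when there is data in the BMQ". It explains that this day "includes the first day for which data is reported via the handheld device, a DCR, or the day of device activation". The wording points to the day the data refer to, not the day they were typed in.

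For Arms A and B the SAP adds that "this is expected to coincide with the Week 1 visit, and the day of their first emicizumab dose". For Arm C it says the start should fall on the Week 1 visit. Neither sentence cuts the period off at that day.

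SAP 2.2.1 describes how data reach the diary (BMQ). Patients complete it "on a handheld device that will be provided to them during the Week 1 visit at the study site". Entries may be back-dated: "the patient is able to enter bleeds and medications for the past 8 days, including the day the entries are made". If the patient could not enter data, "the investigator is able to do so using a data clarification request (DCR; not subject to the previous 8-day data entry window".

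SAP 4.5.1 uses the length of the efficacy period as the offset in the negative binomial model, and SAP 2.3.2 applies the same period to every bleed-related secondary endpoint. The sensitivity analyses in SAP 4.5.4 include one restricted to the first 24 weeks of the efficacy period, but none changes where the period starts.

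**The concern.** The device is handed over at Week 1, the day of first dose in Arms A and B. An entry made that day can refer to any of the 7 days before treatment, and a DCR entry can refer to an earlier day still. Read literally, such an entry moves the start of the period to before treatment, and the bleed enters the numerator.

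The start is also triggered by events. A patient who back-enters a recent bleed gains that bleed and a few days of exposure; a patient with nothing to back-enter gains neither. How often this happens depends on diary habits and site practice, not on treatment.

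At stake is the accuracy of the reported ABR and rate ratio for the primary endpoint and the bleed-related secondaries, and of any count of patients with no treated bleeds.

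**Working it through.** **Inputs.** SAP 2.4 gives ABR 4 on emicizumab and 18 on control, variance 10 times the mean, 28 patients per emicizumab arm, 14 controls, and follow-up of 0.5 years (24 weeks). SAP 2.2.1 gives the window: 8 days including the entry day, so 7 earlier days. The documents do not give the pre-dose bleed rate, the share of patients who back-enter, or how far back a DCR might reach. These are assumptions below.

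**The plan's own figure.** With the variance read on the annual scale, the dispersions are (40 − 4)/4² = 2.25 and (180 − 18)/18² = 0.5. The variance of the log rate ratio is (1/(4 × 0.5) + 2.25)/28 + (1/(18 × 0.5) + 0.5)/14 = 0.1419, so SE = 0.377. Power = Φ(|ln(4/18)|/0.377 − 1.96) = 97.9%. The stated power of more than 90% is reproduced.

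**Seven days back-entered by every patient, 24 weeks of follow-up, pre-dose ABR 18.**
- Follow-up: 168/365.25 = 0.460 years. Expected bleeds: 4 × 0.460 = 1.84 on emicizumab and 18 × 0.460 = 8.28 on control.
- Added: 7/365.25 = 0.0192 years and 18 × 0.0192 = 0.345 bleeds per patient.
- Arm A/B ABR: (1.84 + 0.345)/(0.460 + 0.0192) = 4.56. Control stays at 18. Rate ratio 4.56/18 = 0.253, against 4/18 = 0.222: a 75% reduction instead of 78%.
- This credits each patient with all 7 added days. Under the actual rule the days added lie between 0 and 7. With none added, the ABRs are 4 + 0.345/0.460 = 4.75 and 18.75, and the ratio is still 0.253.

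**Smaller shares and longer follow-up.** With share f, the Arm A/B ABR is (4T + 0.345f)/(T + 0.0192f). T is 0.460 for 24 weeks and 364/365.25 = 0.997 for an assumed 52 weeks; the control ABR stays at 18.

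| Share f | ABR, 24 wk | Ratio, 24 wk | ABR, 52 wk | Ratio, 52 wk |
|---|---|---|---|---|
| 0 | 4.00 | 0.222 | 4.00 | 0.222 |
| 0.2 | 4.12 | 0.229 | 4.05 | 0.225 |
| 0.5 | 4.29 | 0.238 | 4.13 | 0.230 |
| 1.0 | 4.56 | 0.253 | 4.26 | 0.237 |

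**Other assumptions, all patients, 24 weeks.** A pre-dose ABR of 10 or 30 gives an Arm A/B ABR of 4.24 or 5.04 and a ratio of 0.240 or 0.273. A 28-day DCR look-back at pre-dose ABR 18 gives an ABR of 6.0 and a ratio of 0.333.

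**One patient.** No bleeds in 168 days on treatment plus one treated bleed back-dated by 7 days gives a calculated ABR of 1/175 × 365.25 = 2.09 instead of 0.

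**Effect on the test.** Simulations of the negative binomial model with a log-time offset (800 runs per scenario, no stratum term) gave 97.9% power with no back-entry. Power was between 93.8% and 98.5% across the back-entry scenarios. The lowest value came from a 28-day look-back by every Arm A/B patient and no Arm C patient.

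**The case against.** The strongest reply is that the diary is not meant for pre-treatment bleeds. SAP 2.2.1 describes capture during study treatment, and Protocol 4.5.2 gives earlier bleeds their own place in the medical history. The 8-day window exists for completeness. Entries are reviewed by investigator and patient at each clinic visit, and by the sponsor's data manager and Medical Monitor. Nothing invites back-entry on the day of handover. This bears on how often it happens, and it stands: even 20% has no support in the documents. It does not close the gap, because no reviewer is told to remove a pre-dose bleed and the literal rule would count it.

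The SAP does have a rule, the first diary day, and that rule sensibly avoids counting time before bleeds could be captured. What it lacks is a floor.

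A reader might infer more than the text supports:
- That the rule works only against Arms A and B. It applies to Arm C too.
- That emicizumab's count rising by 0.345/1.84 = 19% means its rate rises by 19%. The added days also enter the offset; on the calculation above the ABR rises by 14%.
- That the SAP contradicts itself because Arm C after the switch is anchored to first dose. Those patients already hold an active diary, so a first-diary-day rule could not define their second period.
- That bleeds are counted twice because they also qualified or stratified the patient. This is possible but speculative: prior bleeds enter the model only as the two-level factor, and SAP 4.5.2.5 only lists the comparison with historical rates.

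**Conclusion.** The point holds as a gap in the start rule, and the fix is a cheap improvement. The literal text can count bleeds from before the first dose or the Week 1 visit as on-study bleeds.

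The size is probably small. The full 7-day case moves the rate ratio from 0.222 to 0.253 at 24 weeks, or to about 0.237 at 52 weeks. The longer figure matters because Arm A/B follow-up runs to clinical cutoff, and Protocol 3.1 expects 6 to about 12 months or longer. Only treated bleeds that survive the 72-hour rule count in the primary endpoint, which reduces the effect further. The DCR route has no stated limit, so its size cannot be bounded from the documents.

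The distortion pulls the ratio toward 1 provided back-entry is not concentrated in Arm C. Were it confined to Arm C over 7 days, the ratio could fall at most to 4/18.75 = 0.213. A reader might conclude that the primary test or its type I error is in danger; the figures do not support that. What can be distorted is the reported ABR, the rate ratio and the number of patients with zero treated bleeds.

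**What to change.** In SAP 2.3.1.1 keep the diary rule and add a floor:
- Start the first efficacy period on the later of the first diary day and the date of first emicizumab dose (Arms A and B) or the Week 1 visit date (Arm C).
- For Arm A/B patients who attend Week 1 but are never dosed, use the Week 1 visit date as the floor. The existing one-day rule for withdrawal before Week 1 can stay.
- Exclude bleeds with onset before the start from all on-study bleed endpoints, and list them.
- Classify bleeds on the day of first dose by the recorded bleed time, which the diary already collects.

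The cost is a few sentences and a date filter, with no new data. The downside is that bleeds between randomization and first dose, which an intention-to-treat reading could include, move to a listing. A sensitivity analysis under the current start rule covers that and shows whether the choice matters.
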